#### **5.7.6. Analysis of Quality-of-Life and Health Economic Variables**

The following patient reported outcomes will be summarized and analyzed. Analysis results for exploratory objectives will be included in the final CSR.

##### EuroQol 5 Dimensions 5 Level Questionnaire (EQ-5D-5L)

The health states defined by the 5-dimensional classification will be converted into the corresponding index score. The EQ-5D-5L index will be set to missing if any of the 5 dimensions is missing.

An MMRM model will be fit to the EQ-5D-5L Visual Analog Scale and index scores include the randomization strata (K-L category [2-3 vs. 4]), index joint [hip or knee] and geographic region [North America, Europe]), treatment, visit, treatment-by-visit interaction as fixed effects, and baseline value as a covariate. The least-squares (LS) means for the mean change from baseline to each visit, as well as the LS mean differences between fasinumab doses and placebo and naproxen, with their corresponding standard errors (SEs), p-values and associated 95% confidence intervals, will be provided from the MMRM.

##### 36-Item Short Form Medical Outcome Study Questionnaire, Version 2 (SF-36)

The same analysis used for the EQ-5D-5L will be performed for the subscale scores of the SF-36 using analogous MMRM models. SF-36 subscale scores will be computed if at least 50% of component items are available. The missing items will be imputed by the mean of available items.

##### Health Care Resource Utilization Questionnaire (HCRU)

The utilization of each resource captured on the HCRU will be summarized via descriptive statistics by treatment group for each visit.

### Work Productivity and Activity Impairment-Osteoarthritis (WPAI-OA)

The number and percentage of patients who reported they were working/non-working on Question 1 of the WPAI-OA will be presented by treatment group for each visit. Furthermore, for patients who answered 'YES' to Question 1 at that visit, the absenteeism, presenteeism, work productivity loss and activity impairment scores will also be constructed. The same analysis used for the EQ-5D-5L will be presented for all four scores of the WPAI-OA using analogous MMRM models.

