## 8.2.2.7. Work Productivity and Activity Impairment

The work productivity and activity impairment-osteoarthritis questionnaire is a validated measure of impairments in work and daily activities (Reilly 1993) (Zhang 2010). Patients will complete the questionnaire at time points indicated in Table 1 and Table 2.

A copy of the assessment is provided in the study reference manual.

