#### **4.10. Health Economic Variables**

The following patient reported health economic outcome measures will be recorded:

- HealthCare Resource Utilization (HCRU) including total and type of usage and hospitalizations.
- Change from baseline by visit in the WPAI-OA item and subscores including absenteeism, presenteeism, work productivity loss and activity impairment.

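### SAP 5.7.6 scores WPAI-OA activity impairment only in patients working at that visit, although it is not a work score and SAP 4.10 sets no such limit

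*SAP*

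**What the plan says.** The WPAI-OA part of SAP 5.7.6 begins with a tabulation by arm and visit: "The number and percentage of patients who reported they were working/non-working on Question 1 of the WPAI-OA will be presented". It then sets a condition, "for patients who answered 'YES' to Question 1 at that visit", and under that condition promises that "the absenteeism, presenteeism, work productivity loss and activity impairment scores will also be constructed". The scores go straight into modelling: "The same analysis used for the EQ-5D-5L will be presented for all four scores of the WPAI-OA using analogous MMRM models". The EQ-5D-5L paragraph of the same section defines that model. It analyses change from baseline at each visit with the baseline value as covariate, and gives contrasts of fasinumab with placebo and with naproxen, with standard errors, p-values and 95% confidence intervals.

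Other places describe the score without this condition:

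- SAP 4.10 lists the variable as "Change from baseline by visit in the WPAI-OA item and subscores including absenteeism, presenteeism, work productivity loss and activity impairment". It does not mention employment.
- SAP 5.7 makes the mFAS the default population for efficacy analyses.
- Protocol 8.2.2.7 says the questionnaire "is a validated measure of impairments in work and daily activities" and that "Patients will complete the questionnaire at time points indicated in Table 1 and Table 2". It exempts no one.
- Protocol 6.2.1 and 6.2.2 set no employment criterion and no upper age limit.

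SAP 5.7.7 repeats the 5.7.6 analyses on the FAS. The Year 2 part of SAP 5.7.6 summarizes WPAI-OA descriptively.

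**The concern.** Three of the four scores describe work and have no meaning for someone without a job, so the condition suits them. Activity impairment is the daily-life part of the instrument and does not presuppose employment. Attaching the same condition to it has two effects.

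First, precision is lost. Data from non-working patients are set aside although the questionnaire is given to patients generally.

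Second, the comparison is no longer between the randomized groups. The filter uses the answer at the same visit, so membership can change after randomization, and it can change for reasons linked to pain, function or treatment. Because the model needs a baseline value, a patient contributes to a change score only with a YES at baseline and again at the later visit. A patient who stops working because of the joint would have a recorded activity answer turned into a missing value by the scoring rule, and the MMRM would then treat that value as missing at random.

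**Working it through.** **Reading the texts together.** SAP 5.7.6 contains one scoring sentence. It opens with the working condition and lists four scores, the last being activity impairment. No other sentence in the SAP scores activity impairment for non-working patients, so a programmer following it would leave the score missing for them. SAP 4.10 and the mFAS default in SAP 5.7 point the other way, and no reason for the narrowing is given.

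**Figures in the plan.** None exist for WPAI-OA: no power, rate or sample size. There is nothing to reproduce. The working share is not given either; it is a result still to be tabulated.

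**Size of the precision loss, by assumption.** Let w be the share of patients with a score under the rule, equal across arms, with the same variance in workers and non-workers. Planned numbers from SAP 2.2 are 840 (1 mg Q4W), 600 (1 mg Q8W), 840 (naproxen) and 280 (placebo), in total 2560. These are FAS planning numbers before missing data; mFAS numbers per arm are not stated.

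- Patients kept = 2560 × w.
- Single-visit SE relative to using everyone = 1/√w.
- Detectable standardized difference, Q4W against placebo, 80% power, two-sided 0.05 = (1.960 + 0.842) × √(1/(840w) + 1/(280w)).

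With w = 1 the last line gives 2.802 × √(0.00119 + 0.00357) = 2.802 × 0.0690 = 0.193.

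| w (assumed) | kept | left out | SE ratio | detectable difference |
|---|---|---|---|---|
| 100% | 2560 | 0 | 1.00 | 0.193 |
| 80% | 2048 | 512 | 1.12 | 0.216 |
| 60% | 1536 | 1024 | 1.29 | 0.250 |
| 50% | 1280 | 1280 | 1.41 | 0.273 |
| 40% | 1024 | 1536 | 1.58 | 0.306 |
| 20% | 512 | 2048 | 2.24 | 0.432 |

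The ratio is a single-visit approximation. An MMRM borrows information across a patient's visits, so the planned model's exact figure would differ.

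**How selection could act (every input invented, for direction only).** Suppose 40% work on placebo and 45% on active, because treatment keeps some more impaired patients at work. Let mean impairment be 40 in those who would work in either arm and 60 in the extra workers, with no true effect. The active mean among workers is (0.40 × 40 + 0.05 × 60)/0.45 = 42.2, an apparent 2.2 points against active. With 50% working on active it is (0.40 × 40 + 0.10 × 60)/0.50 = 44.0, or 4.0 points. With equal shares and no exchange of patients it is 0. These are unadjusted visit means; baseline adjustment in the planned model could remove part of the difference.

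**The case against.** Several points on the other side carry weight.

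- **It may be loose drafting.** SAP 4.10 and SAP 5.7 suggest that activity impairment was meant for everyone. That is plausible, but 5.7.6 is the operative scoring instruction and its literal text directs the restricted analysis. It needs correcting under either explanation.
- **The data may not all exist.** The questionnaire is held in the study reference manual, not in these documents. Protocol 8.2.2.7 shows that patients in general complete it, not which items a non-working patient answers. This stands as a caveat, and the fix is therefore worded for patients who answered the item.
- **A shift in employment would be visible.** SAP 5.7.6 tabulates working status by arm and visit. That helps, but counts show only the net shift, not which patients moved, and they do not restore the omitted scores.
- **Little depends on it.** WPAI-OA is exploratory. WOMAC physical function, SF-36 and EQ-5D-5L measure daily function with no employment filter, and Year 2 is descriptive. This stands in full and limits the importance of the point.

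Two stronger readings are tempting. A reader might infer that most patients' activity data are lost. That needs a working share below 50%, which the documents never give; eligibility from age 18 with no upper limit does not settle it. A reader might also infer that randomization is broken for this score. The rule makes selection possible, but nothing in the documents shows that working status differs by arm.

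**Conclusion.** The point holds as a defect in a stated scoring rule. As written, SAP 5.7.6 excludes every non-working patient from the activity-impairment analysis and conditions a randomized comparison on a post-randomization status. This conflicts with the unrestricted definition in SAP 4.10 and with the instrument's scope in the protocol.

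The proportion excluded is unknown. The SE ratio of about 2.24 to 1.12 depends entirely on the assumed 20% to 80% working share, equal variance and a single-visit approximation. Bias is possible in principle and has not been demonstrated.

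The matter is minor. The score lies outside the 29 hypotheses of Protocol 10.1, so no primary or key secondary conclusion changes.

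**What to change.** In the WPAI-OA part of SAP 5.7.6, apply the Question 1 condition to absenteeism, presenteeism and work productivity loss only. State that activity impairment is constructed and modelled for all mFAS patients who answered the item, and for all FAS patients who answered it in the SAP 5.7.7 repeat. Use the same scoring rule for the Year 2 descriptive summaries. If this was always the intention, the same wording removes the ambiguity with SAP 4.10.

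The cost is one clause and a small change to the scoring program. No new data collection is required, alpha is not affected, and the planned tabulation of working status by arm and visit stays as it is.

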### Treatment Satisfaction Questionnaire for Medicine (TSQM)

The same analysis used for the EQ-5D-5L will be performed for the effectiveness, side effects, convenience and global satisfaction domain scores of the TSQM using analogous MMRM models. The missing items will be imputed by the mean of available items.

### **Data from Year 2**

The following endpoints were collected in Year 2:

- WOMAC
- EQ-5D-5L
- WPAI-OA
- Rescue Medication Usage

Summary statistics for the above variables will be presented by treatment group for each visit in Year 2 based on the SAF – Year 2. For numeric endpoints, the raw, change from Year 1 baseline value and change from Year 2 baseline values will be summarized. No models will be fit to the data, nor will any statistical analysis be performed comparing treatment arms or statistics derived from statistical models.

#### **5.7.7. FAS Analysis**

All analyses of the co-primary, secondary, exploratory and PRO endpoints specified in Section 5.7.1, Section 5.7.2, Section 5.7.3, Section 5.7.5 and Section 5.7.6 will also be performed using the FAS. For analyses utilizing the stratification variable geographic region, the strata included will be: North America, Europe and Rest of World.

### **5.8. Analysis of Safety Data**

The analysis of safety and tolerability will be performed on the SAF – Year 1 and SAF – Year 2, as defined in Section 3.4.

The safety analysis will be based on the reported AEs and other safety information (clinical laboratory evaluations, vital signs and 12-lead ECG).

Thresholds for Potential Clinically Significant Values (PCSV) in laboratory variables, vital signs and ECG are defined in Section 10.3.

The summary of safety results will be presented for each treatment group and by visit where applicable.

Day 1 is the first day of investigational product, Day –1 is the day before; there is no Day 0.

The time interval to detect any AEs, including AESIs (except JRs identified at the End of Study Phone Calls), or abnormalities is between the first dose of Year 1 study drug dose up to the end of the Follow-Up Period (either the week 72/Early Termination for those patients not proceeding into Year 2, the week 124E/Early Termination E for those patients proceeding into Year 2 or the Post-Op Joint Replacement Follow-up Visit 2). Any study drug-related SAEs occurring between the end of Follow-Up Period and the End of Study will also be included. Data collected outside this interval will be excluded from the descriptive statistics and identification of abnormalities for laboratory evaluations, ECGs and vital signs. All post-baseline data during the interval will be used in the PCSV analysis including scheduled and unscheduled assessments.

All safety analyses will be performed on Year 1 and Year 2 using the following common rules:

- The Year 1 baseline value will be used for all analyses of the Year 1 On-Treatment, Year 1 and 2 On-Treatment and Year 1 Post-Treatment Periods.
- The Year 2 baseline value will be used for all analyses of the Year 2 On-Treatment and Year 2 Post-Treatment Periods.

### 5.8.1. Adverse Events

The verbatim text, the preferred term (PT), and the primary system organ class (SOC) will be displayed in subject listings. Summaries that include frequencies and proportions of patients reporting AEs will include the PTs and the SOCs.

**Pre-treatment AEs** are defined as AEs that developed or worsened during the Pre-Treatment Period.

**Treatment-emergent AEs (TEAEs)** are defined as AEs that developed or worsened during the On-Treatment Periods.

**Post-treatment AEs** are defined as AEs that developed or worsened more than 4 weeks after the last dose of SC study drug.

The focus of adverse event reporting in the clinical study report will be on TEAEs.

For details on handling missing data and partial dates, see Section 6.4.

Summaries of all TEAEs in each treatment group will include:

- Overview of TEAEs, summarizing number of events and number and percentage of patients within the specified category:
  - Total number of TEAEs
  - Total number of serious TEAEs
  - Total number of treatment-emergent AESIs
  - Patients with any TEAEs
  - Patients with any serious TEAEs
  - Patients with any treatment-emergent AESIs
  - Patients with any TEAEs leading to permanent discontinuation from study drug

- Patients with any TEAEs leading to withdrawal from the study
- Patients with any TEAEs leading to death
- TEAEs by SOC and PT
  - All TEAEs
  - TEAEs by severity: mild, moderate or severe
  - TEAEs resulting in permanent study treatment discontinuation
- Study-Drug related TEAEs by SOC and PT
  - All TEAEs
- TEAEs by PT
  - All TEAEs
  - TEAEs resulting in permanent study treatment discontinuation
- Post-treatment AEs by SOC and PT
  - All post-treatment AEs
  - Post-treatment AEs by severity: mild, moderate or severe
- All Serious TEAEs by SOC and PT
- Post-treatment Serious AEs by SOC and PT
- All serious AEs by SOC and PT
- All non-serious TEAEs by SOC and PT
- Post-treatment non-serious AEs by SOC and PT
- All non-serious AEs by SOC and PT
- All AEs by SOC and PT
  - All AEs
  - All AEs by severity: mild, moderate or severe
- Deaths

Counts will be provided according to treatment group for each PT within each SOC. Percentages will be calculated using the number of patients in each treatment group using the respective SAF.

Primary SOC's will be sorted by descending frequency of the 'Fasinumab 1 mg SC Q4W' treatment group. Within each primary SOC, PTs will be sorted by decreasing frequency of investigational product.

A second type of table with counts of each primary SOC in decreasing order of frequency will be provided. A third type of table with counts of each PT in decreasing order of frequency will also be provided.

The above TEAE analyses will be performed for the Year 1 On-Treatment Period, Year 2 On-Treatment Period, Year 1 and 2 On-Treatment Period, Year 1 Post-Treatment Period and Year 2 Post-Treatment Period using the corresponding analyses sets specified in Section 5.

The following listings will be included:

- AEs leading to death
- TEAEs leading to permanent discontinuation from study drug (not applicable to post-treatment AEs)
- TEAEs leading to withdrawal from study
- Patients with Serious TEAEs
- AESIs
- Deaths
- All Cause Joint Replacements
- Pre-treatment AEs
- Post-treatment AEs

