#### **3.4. The Safety Analysis Sets (SAF)**

The Year 1 safety analysis set (SAF – Year 1) includes all randomized patients from the FAS who received any study drug; it is based on the treatment received (as treated). Treatment compliance/administration and all clinical safety variables for Year 1 will be analyzed using the

SAF – Year 1 including patients randomized to fasinumab 1 mg Q4W, fasinumab 1 mg Q8W, naproxen, and placebo.

The Year 2 safety analysis set (SAF – Year 2) includes all patients who received at least 1 dose of the Year 2 study drug; it is based on the treatment received during Year 2 (as treated). Treatment compliance/administration, all clinical efficacy and safety variables and all patient reported outcomes from Year 2 will be analyzed using the SAF – Year 2.

The following rules will be used to define the actual treatment a patient received:

- Patients randomized to either the placebo or naproxen arm who receive at least one dose of active fasinumab during Year X will be considered as treated with fasinumab 1 mg Q8W and classified in the fasinumab 1 mg Q8W treatment arm for the purpose of analysis using the SAF – Year X, where X = 1 or 2.
- Patients randomized to the placebo arm who have not received any active fasinumab injections but were ever dispensed active naproxen during Year 1 will be considered as treated with naproxen and classified in the naproxen treatment arm for the purpose of analysis using the SAF – Year 1.
- For patients randomized to either the fasinumab 1 mg Q8W or Q4W arms, as treated is defined to be as randomized and they will be classified in the treatment arm they were randomized to for the purpose of the analysis using the SAF – Year X, where X = 1 or 2, with the following exceptions:
  - In Year 1, if a patient receives no doses of active naproxen or fasinumab, then the patient will be considered as treated with placebo and classified in the placebo treatment arm for the purpose of analysis using the SAF – Year 1.
  - In Year 1, if a patient receives no doses of fasinumab but were ever dispensed any active dose of naproxen, then the patient will be considered as treated with naproxen and classified in the naproxen treatment arm for the purpose of analysis using the SAF – Year 1.
  - In Year 2, if a patient receives no doses of fasinumab, then the patient will be considered as treated with naproxen prn and classified in the naproxen prn treatment arm for the purpose of analysis using the SAF – Year 2.

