- Number and percentage of patients using at least one prohibited medication during the Year 1 and Year 2 Follow-up Periods separately.
- Number and percentage of patients with at least one prohibited NSAID use during the Year 1 and Year 2 Treatment Periods separately.
- Number and percentage of patients with at least one prohibited NSAID use during the Year 1 and Year 2 Follow-up Periods separately.
- Number of days patients used prohibited medications during the Year 1 and Year 2 Treatment Periods separately.
- Number of days patients used prohibited NSAID medications during the Year 1 and Year 2 Treatment Periods separately.

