## 5. STATISTICAL METHODS

For continuous variables, descriptive statistics will include the following: the number of patients reflected in the calculation (n), mean, median, standard deviation, minimum & maximum and 1st & 3rd quartiles (Q1 & Q3).

For categorical or ordinal data, frequencies and percentages will be displayed for each category.

**Period of observation** – Unless otherwise stated, analysis of all safety variables captured at multiple visits will be analyzed by the following observations periods:

- The Pre-Treatment Period is defined as the time from signing the ICF to before the first dose of study drug in Year 1.
- The Year 1 On-Treatment Period is defined as the day from first dose of Year 1 study drug through the day of last Year 1 SC dose + 4 weeks for those patients not proceeding into Year 2, or up to the first dose of Year 2 study drug for those patients proceeding into Year 2. Summaries for the Year 1 On-Treatment Period will be based on the SAF – Year 1.
- The Year 1 Post-Treatment Period is defined from the end of the Year 1 On-Treatment Period to the Week 72/Early Termination Visit for those patients not proceeding into Year 2. Summaries for the Year 1 Post-Treatment Period will be based on the SAF – Year 1.
- The Year 2 On-Treatment Period is defined as the day from first dose of Year 2 study drug through the day of last Year 2 SC dose + 4 weeks for those patients proceeding into Year 2. Summaries for the Year 2 On-Treatment Period will be based on the SAF – Year 2.
- The Year 1 and 2 On-Treatment Period is defined as day from first dose of Year 1 study drug through the day of last SC dose + 4 weeks. Summaries for the Year 1 and 2 On-Treatment Period will be based on both the SAF – Year 1 and SAF-Year 2.
- The Year 2 Post-Treatment Period is defined from the end of the Year 2 On-Treatment Period to the Week 124E/Early Termination E Visit for those patients proceeding into Year 2. Summaries for the Year 2 Post-Treatment Period will be based on the SAF – Year 2.

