### **5.3. Prior/Concomitant Medications**

Summaries will present patient counts (and percentages) for all medications, dictionary coded by WHO, by decreasing frequency of the overall group incidence (or fasinumab 1mg Q4W group incidence in tables where the overall is not presented) of ATC followed by ATC level 2, ATC level 4 and preferred term. In case of equal frequency across anatomic or therapeutic categories, alphabetical order will be used. Patients will be counted once in each ATC category (anatomic or therapeutic) linked to the medication but may be counted several times for the same medication.

The following will be summarized:

- All prior medications will be summarized by treatment group and overall, based on the SAF – Year 1 and the SAF – Year 2 separately.
- All concomitant medications taken during the Year 1 On-Treatment Period will be summarized by treatment group based on the SAF – Year 1. Similarly, all concomitant medications taken during the Year 2 On-Treatment Period will be summarized by treatment group based on the SAF – Year 2.
- All Post-treatment medications taken during the Year 1 Post-Treatment period will be summarized by treatment group based on the subset of patients in the SAF – Year 1 who do not continue into Year 2. For patients who continue into Year 2, all concomitant medications taken during the Year 2 Post-Treatment period will be summarized by treatment group based on the SAF – Year 2.

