### **5.4. Prohibited Medications**

Summaries of prohibited medications will present patient counts (and percentages) for all prohibited medications, dictionary coded by WHO, by decreasing frequency of the overall group incidence (or fasinumab 1mg Q4W group incidence in tables where the overall is not presented) of ATC followed by ATC level 2, ATC level 4 and preferred term. In case of equal frequency across anatomic or therapeutic categories, alphabetical order will be used. Patients will be counted once in each ATC category (anatomic or therapeutic) linked to the medication but may be counted several times for the same medication. The following will be provided:

- All prohibited medications taken during the Pre-Treatment Period will be summarized by treatment group and overall, based on the SAF – Year 1 and SAF – Year 2 separately.
- All prohibited medications taken during the Year 1 Treatment and Follow-up Periods will be summarized by treatment group based on the SAF – Year 1. An analogous analysis will be performed for Year 2 Treatment and Follow-up Periods based on the SAF – Year 2.
- All prohibited NSAID medications taken during the Year 1 Treatment and Follow-up Periods will be summarized by treatment group based on the SAF – Year 1. An analogous analysis will be performed for Year 2 Treatment and Follow-up Periods based on the SAF – Year 2.

- The total number of days using prohibited NSAIDs during the Year 1 Treatment and Follow-up Periods (before AA for patients with AA) will be summarized by treatment group based on the SAF – Year 1. An analogous analysis will be performed for the Year 2 Treatment and Follow-up Periods based on the SAF – Year 2.
- The number of days from the last dose of study drug in Year 1 to the first NSAID dose will be summarized in the subset of patients in the SAF – Year 1 who do not continue into Year 2. Similarly, the number of days from the last dose of study drug in Year 2 to the first NSAID dose will be summarized based on the SAF – Year 2.

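### Year 1 Post-Treatment AE percentages use the whole SAF – Year 1 as denominator, although only patients who do not enter Year 2 have that period

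*SAP*

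**What the plan says.** - **The period.** SAP Section 5 runs the Year 1 Post-Treatment Period from the end of Year 1 on-treatment time "to the Week 72/Early Termination Visit for those patients not proceeding into Year 2". For patients who do proceed, Year 1 on-treatment time lasts until their first Year 2 dose, so they have no Year 1 post-treatment time.
- **The analysis set.** The same bullet states: "Summaries for the Year 1 Post-Treatment Period will be based on the SAF", meaning the SAF – Year 1. Under SAP 3.4 that set "includes all randomized patients from the FAS who received any study drug", whether or not the patient later enters Year 2. Protocol 10.4.4 has the same period and the same set.
- **The AE denominator.** SAP 5.8.1: "Percentages will be calculated using the number of patients in each treatment group using the respective SAF". It then runs the AE tables for five periods, including the Year 1 Post-Treatment Period, "using the corresponding analyses sets specified in Section 5". No AE text narrows the denominator.
- **A different rule for the same period.** SAP 5.3: "All Post-treatment medications taken during the Year 1 Post-Treatment period will be summarized by treatment group based on the subset of patients" of the SAF – Year 1 that does not go on to Year 2. The last bullet of SAP 5.4 applies the same restriction to the time from last dose to first NSAID.
- **Prohibited medication.** SAP 5.4: "All prohibited medications taken during the Year 1 Treatment and Follow-up Periods will be summarized by treatment group based on the SAF", again Year 1. SAP 4.4 lists a separate follow-up figure without naming a denominator: "Number and percentage of patients using at least one prohibited medication during the Year 1 and Year 2 Follow-up Periods separately".

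**The concern.** A patient who enters Year 2 cannot have a Year 1 post-treatment AE under the SAP's own period definition. The AE tables nevertheless count that patient in the denominator, which has the same effect as recording no event in a period the patient never had. The printed percentage is therefore lower than the percentage among patients who have the period, in every arm with Year 2 entrants. These tables are where events emerging after dosing stops are displayed, and protocol 1.2 calls off-treatment follow-up important for understanding benefit and risk. In addition, AE and medication tables for one and the same period would carry different Ns.

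**Working it through.** The plan gives no figure on this point, so there is nothing to reproduce. The check is algebra with illustrative numbers.

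**Inputs**
- N: patients in an arm of the SAF – Year 1. The planned 840 for fasinumab 1 mg Q4W (SAP 2.2) serves as illustration.
- x: patients with a Year 1 post-treatment AE. By the period definition, none of them entered Year 2. Here x = 50 is an assumption.
- q: share of the arm's SAF – Year 1 that enters Year 2. It is not in the documents; 10% to 40% is assumed.

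**Step 1: the factor**
- SAP percentage = x / N.
- Percentage among patients who have the period = x / [N(1 − q)].
- Ratio of the first to the second = 1 − q, whatever x and N are. It equals 1 only if nobody in the arm enters Year 2.

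**Step 2: numbers** (SAP rule: 50/840 = 6.0%)

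| q (assumed) | Patients with the period | Percentage among them | Relative understatement |
|---|---|---|---|
| 10% | 840 × 0.90 = 756 | 50/756 = 6.6% | 10% |
| 30% | 840 × 0.70 = 588 | 50/588 = 8.5% | 30% |
| 40% | 840 × 0.60 = 504 | 50/504 = 9.9% | 40% |

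**Step 3: comparison between arms**

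If two arms have the same true percentage, their apparent ratio is (1 − q of the first) / (1 − q of the second).
- Equal q gives 1, so ratios are unchanged.
- With a true 10% in both arms, assumed q of 40% and 20% shows 6.0% against 8.0%, a ratio of 0.75. Reversing the shares gives 8.0% against 6.0%, a ratio of 1.33.

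**Step 4: do the documents give a reason for q to differ?**

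Enrolment timing gives one for Q8W only. Protocol 5.1.3 plans the share randomized before Amendment 5 as 240/840 = 240/840 = 80/280 = 2/7 (28.6%) in Q4W, naproxen and placebo, and 0/600 in Q8W. Protocol 6.2.3 closed Year 2 to Week 52 visits from 26 March 2020.

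Let e and s be the entry shares before and after Amendment 5, assumed common to all arms:
- q(Q8W) = s; q(Q4W) = (2/7)e + (5/7)s; q(Q4W) − q(Q8W) = (2/7)(e − s).
- A 10-point difference between e and s moves q by (2/7) × 10 = 2.9 points.
- s = 30%, e = 20%: q(Q4W) = 27.1%; Q8W:Q4W ratio = 0.700/0.729 = 0.96.
- s = 30%, e = 40%: q(Q4W) = 32.9%; ratio = 0.700/0.671 = 1.04.

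The documents do not say which of e and s is larger. Timing alone gives no gap among Q4W, naproxen and placebo.

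**Step 5: the other post-treatment tables**

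Everyone in the SAF – Year 2 received Year 2 drug, so the Year 2 Post-Treatment tables do not have this mismatch.

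**The case against.** The strongest defence is that events in a named period over a named set is a coherent quantity: the share of treated patients with an AE in that period. Both documents define it openly and alike. That is true. It is still not a randomized comparison over common follow-up, because entrants' post-treatment events are moved to the Year 2 tables, and it is not an incidence among patients who have the period.

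Other objections stand and limit the point:
- The missing N is recoverable. SAP 5.3 gives counts and percentages on exactly the restricted subset, which together yield N by arm, up to rounding. The disposition table in SAP 5.5.2 also gives Year 2 enrolment by arm, though on mFAS and FAS denominators and defined by eligibility and consent rather than dosing.
- Every input to the size (q, e, s, the 50 patients) is assumed.
- The restricted subset is not a clean at-risk set. It is selected after randomization, since protocol 6.2.3 bars patients who permanently stopped study drug from Year 2. Follow-up within it is unequal: a last dose at Week 48 leaves 72 − 52 = 20 weeks, and one at Week 4 leaves 72 − 8 = 64. It also includes patients who left before the period began. One might suppose these are few, but no text says so.

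A reader might infer that all Year 1 Follow-up percentages share the error. The documents do not support that. SAP 5.8.4 (orthostatic hypotension), 5.8.6 (examinations) and 5.8.7 (joint replacements) state no denominator, and the general reference to the SAF in SAP 5.8 does not settle one. The SAP 5.4 sentence on prohibited medication can be read as one summary over treatment and follow-up combined, and for that the full SAF – Year 1 is right because every member has a treatment period.

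**Conclusion.** The mismatch is real for the Year 1 Post-Treatment AE tables. The factor (1 − q) is exact relative to SAF – Year 1 patients who do not enter Year 2; its size depends on a q that the documents do not report. The consequence is modest. The tables are descriptive, and SAP 5.8.1 puts the focus on treatment-emergent AEs. Counts, listings and the time-to-event analyses of arthropathy and joint replacement do not change.

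A reader might infer that the rule favours fasinumab or distorts the comparison between arms. Nothing in the documents shows this: equal entry shares leave ratios unchanged, and the one documented reason for unequal shares affects only Q8W against the other arms, by about 4% either way under the assumed shares, in an unknown direction. The point is worth correcting because the right rule already stands in SAP 5.3.

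**What to change.** - In SAP 5 and 5.8.1, use for every Year 1 Post-Treatment AE table the SAP 5.3 denominator, SAF – Year 1 patients who do not go on to Year 2, and show that N by arm.
- In SAP 4.4 and 5.4, use the same denominator for the separate Year 1 Follow-up percentages of prohibited medication and NSAID use. A combined treatment and follow-up summary may keep the full SAF – Year 1.
- In SAP 5.8.4, 5.8.6 and 5.8.7, simply show the same N beside Year 1 Follow-up percentages.
- State that the subset is selected after randomization, has unequal post-treatment follow-up, and contains an unstated number of patients with no post-treatment observation, so arm comparisons in these tables remain descriptive.
- Record the departure from protocol 10.4.4 in SAP 1.2.3, which now reports no modifications.

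The cost is a few sentences of SAP text and an extra N row in the tables. No new data are needed, and nothing changes for efficacy or type I error.
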